*The proposed study builds upon the momentum, resources, and research infrastructure of our pilot work to test the larger-scale and sustained impact of COPE on infant's and mothers' obesity outcomes, and to study key mechanisms of maternal and social transmission on infants' obesity risk.* Specifically, 300 low-income mothers/infants enrolled in Healthy Families America HVP will be recruited and enrolled in the study, for an effective final sample of 200 mothers/infants. Based on standard HVP procedures, mothers/infants will be matched to highly trained home visitors (nurses) based on their ethnicity/race and language preferences. Home visitors, in turn, will be randomly assigned to deliver the standard HVP curriculum only or the standard HVP curriculum + COPE as part of their weekly home visits for two years of HVP services. Comprehensive assessments of mothers/infants will be conducted at enrollment and after 6 and 12 months of intervention.

**Specific Aim 1 (maternal and infant outcomes).** Test the direct effects of COPE on infants and mothers' weight, metabolic risks, diet/energy intake, and physical activity. This will be accomplished by comparing changes in body weight, metabolic markers, and eating and activity-related behaviors between infants/mothers across study arms (HVP only vs. HVP+COPE). These results will indicate whether HVP is an effective infrastructure for primary and secondary obesity prevention.

**Specific Aim 2 (maternal transmission).** Test whether breastfeeding and maternal diet and activity, feeding practices, and food insecurity mediate the effect of COPE on infants' outcomes. This aim will test mechanisms of maternal transmission on infants' obesity risks.

**Specific Aim 3 (social transmission).** **Aim 3** is two-pronged. **Aim 3a** tests the direct effect of HVP+COPE (vs. HVP only) on the characteristics of the social and community networks that surround mothers and infants (i.e., the density, composition, and quality of "health support networks"). **Aim 3b** tests whether the characteristics of social networks mediate the effects of COPE on maternal and infant outcomes. These findings will indicate if HVP obesity prevention efforts can alter and/or activate social network mechanisms.

**Secondary Aim.** Conduct a real-life economic analysis (costs, cost-savings, and non-monetary benefits) of integrating COPE into existing HVPs.

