2. **Social experiential activities (Table 5)** were selected in response to: our theoretical framework that emphasizes social network influences; our pilot work that highlights existing social network barriers to behavior change; and families’ desire to learn through hands-on, social activities. These activities are already built into the service infrastructure at Antelope Valley Partners for Health, are integrated across all key content areas of COPE, and will be promoted to participants in the intervention arm (but not to participants in the control arm) by their home visitor. Participation by study participants will be monitored and recorded by activity staff. One central purpose of the communal activities is to foster new, yet sustainable social and community connections that will provide increased healthy behavior role models and social support for mothers. This will be achieved through activities that provide a context for repeated social connection among consistent groups of COPE participants in their neighborhoods, and through activities designed to foster group learning, discussion, and shared experiences that are aligned with the individual didactic learning in home. These social activities are similar to those delivered as part of the *National Institute of Food and Agriculture’s Expanded Food and Nutrition Education Program*.

Table 5. Description of COPE experiential and communal activities	
Communal cooking	Advance meal preparation to promote home cooking using foods from WIC/food bank, and decrease reliance on fast-food. Gatherings are lead by [name] (Site Culinary Program Coordinator) and take place in the Wellness Homes operated by our partner (Resources & Environment section).
Community gardening	Mariposa master gardeners teach parents/children gardening techniques (planting, growing and harvesting fruits and vegetables). Gardens are located on Wellness Homes’ grounds. Families tend local gardens with other families.
Food management	Classes to improve food resource management practices such as purchasing, selecting, or otherwise obtaining; preparing; and storing foods to increase sustained availability of healthy foods throughout the month. This material is delivered in local grocery stores and markets.
Mobile food demos	Food demonstrations hosted in neighborhood farmers markets to provide convenient and accessible cooking and food preparation demonstrations using fresh products from local farmers markets.

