### B. Potential Risks/Adverse Events and Procedures Used to Minimize the Risks

For purposes of monitoring and reporting adverse events, the following definitions will be used:

**Adverse event (AE):** any untoward medical occurrence that may present itself during treatment or administration of an intervention, and which may or may not have a causal relationship with the treatment. Adverse events could arise from the study (e.g., breach of confidentiality) or could arise because of the population under study (e.g., a mother reports extensive use of drugs).

**Serious adverse event (SAE):** Any medical occurrence that results in death; is life-threatening; requires inpatient hospitalization or prolongation of existing hospitalizations; creates persistent or significant disability/incapacity, or a congenital anomaly/birth defect. Such an event could include suicidal ideation or attempted drug overdose or withdrawal, etc.

**Adverse events monitoring.** Each participant (mother and infant) will be evaluated for any adverse events. All events will be graded by their attribution (unrelated to protocol; or possibly, probably, or definitely related to protocol). Any event reported to the Principal Investigators or to designated research associates by the subjects or Antelope Valley Partners for Health nursing and medical staff, which also meets the event criteria, will be carefully documented in a report submitted to the IRBs. The report will include a description of the event; when and how it was reported; any official charts, records, or documentation to corroborate the event or the reporting of the event; and an action plan to prevent future occurrences. All adverse events will be graded as mild, moderate, or severe. Any severe and/or unanticipated adverse event will be immediately reported to the IRBs (within 48 hours of occurrence or recognition) and NIH. All adverse events will be summarized annually and submitted to the IRBs and NIH. Any action resulting in a temporary or permanent suspension of this study (e.g., IRB actions) will be reported to the NIH.

**Physical risks.** There are minimal physical risks added from participating in this study. All lifestyle dietary and physical activities suggested are in line with national guidelines. Recommended physical activities are low impact and unlikely to create discomfort for participants.

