**Psychological risks.** Though none of the questionnaires contain items that are particularly sensitive, personal, or potentially upsetting, it is possible that a participant may become upset thinking about some of the questions or topics in this study. Trained assessors will be conducting the assessment sessions to address any potential incident. All participants will be informed that they are free to refuse to answer any particular questions or questionnaires. They will also be informed that they can withdraw from the study at any time without penalty. Staff will immediately report any AEs connected to the implementation of the intervention to Drs. [name] and [name] who will keep a log of AEs and SAEs. Drs. [name] and [name] will file a written report within 24 hours of being notified to the IRB, whether the event relates to the project or not. As part of this process, members of the IRB committee review the event and determine whether the event is directly related to project procedures so that it can be determined whether procedures need to be modified to avoid a similar AE in the future. Whether the event is related to the project, we will keep a log to provide information about all AEs in annual progress reports to the IRB and NIH. Drs. [name] and [name] will monitor outcomes for AEs, and outcome information will be entered into a log for inclusion in reports to the IRB and NIH.

**Social risks.** There are no social risks for participating in this study.

**Legal/other risks.** None.

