2. The PIs will implement and monitor procedures to ensure that each mother provides informed consent and that all data remains confidential. This will also include a rigorous data management protocol to optimize data entry, accuracy/checking, and retrieval. Data will be stored in password-protected files accessible only to the investigators and staff under their supervision. In the database, only an ID code number will identify subjects. A list linking names and other identifiers with their ID codes will be stored in a separate file with a separate password. All original paper surveys and case report forms will be stored in locked file cabinets. The PIs will review all data collection forms for completeness and accuracy of the data and for protocol compliance. In the case of a breach of confidentiality or other adverse event, the Principal Investigators will report the event to the IRB and the appropriate NIH officials, and appropriate procedural changes will be implemented to prevent future breaches or adverse events.
3. An internal committee comprised of the projects' Principal Investigators (Dr. [name] will serve as the chair of the committee and [name] will act as clinical training and supervisor chair) and the On-Site Project Director ([name] at Antelope Valley Partners for Health) will meet quarterly to assess: participant recruitment, accrual, and retention; data quality and timeliness; participant risk versus benefit; and the development of external conditions that could potentially affect the study. Significant problems or adverse events will be reported immediately to the USC and UAB IRBs, NIH, or FDA (if relevant).
4. As part of their training for the study, all personnel who will interact with subjects will receive instruction in the completion of an adverse event reporting form. In response to any adverse event, these forms will be completed promptly and returned to the corresponding study team supervisor, who in turn will report the information to the Principal Investigators.

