5. An external Data Safety Monitoring Board (DSMB), not connected to USC, UAB or the research project, will convene twice annually, via teleconference, to review the progress of the study, ensure adequate recruitment of minority subjects, and to monitor safety concerns. Key members of the research team will co-participate in the conference calls. The DSMB will consist of five to-be-named individuals from outside USC: (1) a home visitation program consumer (parent, most likely a mother) (2) a child services advocate; (3) a layperson; (4) a home visitation program stakeholder; (5) a health disparities researcher and (6) a mental health professional. The DSMB will meet by phone conference two times within each of the project's 5 years. Their function will be to review the progress of the study, ensure adequate recruitment of minorities into the sample, and monitor the study with respect to the safety and well-being of the research patients.
6. Safety officer. [name], DO is a pediatrician at the Antelope Valley Community Clinic. [name] will serve as safety officer on this project to ensure the protection, safety and satisfaction of mothers and staff throughout the many facets of the project. [name] will serve as contact-person to family participants, service providers, and all project staff to report problems or areas of concern regarding project implementation for resolution with investigators.

**Additional protections for pregnant women, human fetuses, and neonates involved in research.** This study involves parents and their infants (6mo at enrollment). This research does not involve women who are pregnant. If a mother becomes pregnant during the study, she will continue to receive HVP services, but she will not be involved in the study.

**Potential benefits of the proposed research to human subjects and others.** The potential benefits of this study include better management of postpartum weight-loss among mothers involved in home visitation programs and healthier growth trajectories for their infants. This study will also help researchers and professionals understand how home visitation programs can be used as a vehicle for early childhood obesity prevention. Participants will benefit by receiving a nutrition and physical activity module at no cost. Thus, the benefits of this project to the individual and society greatly outweigh the risks.

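### Adverse events have no scheduled, arm-neutral elicitation, so event rates by arm may differ through ascertainment as well as risk

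*Combined protocol and SAP*

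**What the plan says.** **How events are found**

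- Protection of Human Subjects, section B, Adverse events monitoring: "Each participant (mother and infant) will be evaluated for any adverse events". No form, interval, look-back period or assessor follows. The documentation step that comes next concerns events brought to the PIs or research associates "by the subjects or Antelope Valley Partners for Health nursing and medical staff".
- Same section, Psychological risks: "Staff will immediately report any AEs connected to the implementation of the intervention". The sentences after it ask for an IRB report and a log of all events, related or not.
- Section D, Monitoring plan item 4: "all personnel who will interact with subjects will receive instruction in the completion of an adverse event reporting form". The form is filled in when an event has occurred.
- Section D, item 6: the safety officer "will serve as contact-person to family participants, service providers, and all project staff to report problems or areas of concern" about how the project is being carried out.
- Section C.5, Table 6: no adverse-event row at any time point.

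**How contact compares between arms**

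- Section A: both arms receive their curriculum "as part of their weekly home visits". Section C.1: assessment workers are blind to assignment.
- Section C.4: communal cooking, gardening, classes and food demonstrations "will be promoted to participants in the intervention arm (but not to participants in the control arm) by their home visitor". Also: "Participation by study participants will be monitored and recorded by activity staff".
- Section C.2: in the pilot, fewer mothers dropped out with COPE. No figures are given.

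**How event rates are used**

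- Section D, Safety reviews: the annual report judges whether event rates match what was assumed beforehand. Item 5 gives the DSMB a safety-monitoring role. Section E puts adverse events in the posted summary results.

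**The concern.** Spontaneous reporting finds an event only if somebody notices it and passes it on. Here the chance of being noticed may depend on the arm. Families who attend the COPE activities see more staff, and families who stay longer are observed longer. Home visitors, who have the most contact, know which curriculum they deliver, and that knowledge can push reporting either way.

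The consequence runs in two directions. Extra contact could make a harmless module look as if it causes more events. Equally, a genuine COPE excess could be set aside as an artefact of contact, because nothing in the plan would separate the two. The module changes infant feeding, and about half the mothers are expected to be 18 or younger (Protection of Human Subjects, section A), so the PIs and DSMB should be able to read event rates by arm.

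**Working it through.** The documents give no adverse-event rate, no frequency for the communal activities and no attendance figure. There is no planned figure to reproduce. The check is first textual, then an illustration under stated assumptions.

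**Step 1. Is any route scheduled and identical in both arms?**

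| Route | What starts it | Same question, same time, both arms? |
|---|---|---|
| Evaluation of each participant (section B) | Not stated | Intended for all, but no instrument or timing |
| Reports by participants or site staff (section B) | Someone reports | No |
| Staff form (section D, item 4) | An event already noticed | No |
| Safety officer (section D, item 6) | Someone makes contact | No |
| Table 6 assessments | Calendar | Yes, but no adverse-event item |

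The one calendar-driven, blinded contact carries no adverse-event question. Depression illustrates the gap: section B gives suicidal ideation as an example of a serious event, but Table 6 lists post-partum depression at baseline only.

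**Step 2. Does opportunity differ by arm?** Weekly visits and assessments are common to both. The communal activities are promoted to COPE families only. Lower dropout with COPE, if repeated, adds observation time in that arm.

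**Step 3. How large could the effect be?** Assume equal true risk. Let *q* be the chance that one contact captures a current event, *w* the weekly visits during which it stays reportable, and *m* the proportional extra contact in COPE.

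- Captured, HVP only: 1 − (1 − q)^w
- Captured, COPE: 1 − (1 − q)^(w(1 + m))

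All three inputs are assumptions. On a base of 52 visits a year, m = 25% is 13 extra contacts (13/52), 50% is 26 (26/52) and 92% is four a month (48/52). Worked case, q = 0.25, w = 1, m = 50%: 0.250 against 1 − 0.75^1.5 = 0.350, a ratio of 1.40. With w = 4: 0.684 against 1 − 0.75^6 = 0.822, a ratio of 1.20.

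| q | w = 1: m = 25 / 50 / 92% | w = 4: m = 25 / 50 / 92% |
|---|---|---|
| 0.05 | 1.24 / 1.48 / 1.88 | 1.22 / 1.43 / 1.76 |
| 0.10 | 1.23 / 1.46 / 1.83 | 1.19 / 1.36 / 1.61 |
| 0.25 | 1.21 / 1.40 / 1.70 | 1.12 / 1.20 / 1.30 |
| 0.50 | 1.16 / 1.29 / 1.47 | 1.03 / 1.05 / 1.06 |
| 0.90 | 1.05 / 1.08 / 1.10 | 1.00 / 1.00 / 1.00 |

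The model treats a group session as equal to a home visit and assumes that COPE families attend, so it leans toward a larger effect.

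**Step 4. Would it produce a false signal?** Take 100 per arm (200/2) or 150 per arm (300/2), with 1:1 allocation assumed. Divide by a design effect of 1, or by the plan's own 1.4 or 1.8. Assume recorded control risks of 6% or 18% and a spurious ratio of 1.25, giving 7.5% or 22.5% in COPE. The chance of two-sided p < 0.05 runs from 5% (6%, 100 per arm, design effect 1.8) to 16% (18%, 150 per arm, design effect 1). The likelier harm is a comparison that cannot be interpreted, rather than a significant false alarm.

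**The case against.** Several stronger readings are tempting, and the documents do not support them.

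- *That events are captured only when staff file a form.* Section B promises evaluation of every participant and accepts reports from participants, and families can approach the safety officer. The defect is that the evaluation is unspecified, not that it is absent.
- *That HVP-only families fall outside the reporting duty.* The sentence about events connected with the intervention sits under Psychological risks. The text after it covers events whatever their relation to the project, and section B grades attribution to include unrelated events. The wording is loose but does not exempt an arm.
- *That the trial cannot show harm at all.* Infant weight, length and diet are scheduled alike in both arms. Section C.2 continues to monitor program benchmarks that include emergency department visits and child abuse or neglect. Deaths and admissions should also depend less on casual contact. These sources are real, though no passage routes the benchmarks into the adverse-event log or the DSMB review.
- *That activity staff are extra adverse-event reporters.* They are said only to record participation. Whether they receive the form training is not stated.
- *That Children's Bureau families are under-reported in one arm.* Section B names only Antelope Valley Partners for Health staff, but nothing places the other site's families mainly in one arm.

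It is also fair that Safety reviews names no between-arm comparison, and that near-complete capture at weekly visits would leave extra contact little to add. What stands after all this is that no scheduled, common question exists and that opportunity for detection may differ by arm.

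**Conclusion.** The concern holds in a limited form. The plan states an intention to evaluate every participant without saying how or when, and everything else is spontaneous. With additional activities offered to one arm, unblinded home visitors and possibly unequal dropout, event rates by arm may mix ascertainment with risk.

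The extra contact by itself would push counts up in COPE; knowledge of the arm could act either way. The size cannot be determined from the documents. The range of 1.00 to 1.88 is a sensitivity display resting on assumed capture probabilities and contact frequencies, not an estimate. This should be corrected because event rates are judged yearly, reviewed by the DSMB and posted, and the correction uses assessments that already exist.

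**What to change.** 1. Add an adverse-event row to Table 6. At each existing assessment, have the blinded assessment workers ask the same short fixed list in both arms, for mother and infant, covering the time since the last assessment: hospital admission, emergency visit, injury, feeding or growth concern, and any other event.
2. Keep the item 4 forms and other spontaneous reports for prompt reporting. Record the source of every event.
3. Show the PIs and DSMB two sets of figures by arm and per person-time: solicited events, and all events combined. Relying on solicited answers alone would lose events in families who leave before the next assessment. Dropout is put at 25% in section C and may differ by arm.
4. Reword the Psychological risks trigger to cover all adverse events in both arms, and name Children's Bureau staff among the reporters in section B.

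**Cost.** A few minutes per assessment, more minor events recorded, and some recall error. Recall depends on the interval: six months if assessments fall at 6 and 12 months as sections C.1 and C.6 say, but twelve (18 − 6) if they follow the 6- and 18-month columns for the interview measures in Table 6. Common questions equalize the opportunity to report; they do not remove any effect of mothers knowing which curriculum they receive.

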#### **E. ClinicalTrials.gov Requirements**

The project will be registered in [ClinicalTrials.gov](https://clinicaltrials.gov) no later than 21 days after the first subject is enrolled. Reporting of summary results information (including adverse events) will be reported no later than 1 year after the completion date. The [ClinicalTrials.gov](https://clinicaltrials.gov) registry number (also known as NCT number), brief lay public title, and a certification that all required submissions to [ClinicalTrials.gov](https://clinicaltrials.gov) were completed will be provided in progress reports. The PIs ([name] at UAB and [name] at USC) will assume responsibility for these aspects of the trial.

## **MINORS AS RESEARCH SUBJECTS**

The research team is well trained and experienced in conducting research in children. [name] (MPI) has been trained in Pediatric and Child Psychology and she has been a member of the children's Institutional Review Board (IRB) for several years at the Women and Children's Hospital in Buffalo, NY. She will ensure the quality of the treatment implementation. The involvement of minors as participants in this research is in compliance with all subparts of 45 CFR Part 46 as well as with Federal laws and regulations.

